11.3. Posting of Information on Public Registries

Study information from this protocol will be posted on Clinicaltrials.gov and www.pactr.org.

11.4. Publication

PATH will work with the PI and other relevant personnel at MRCG at LSHTM on the publication of the complete Phase 3 study outlined in this protocol in a timely fashion. Primary publication of the trial results will be shared between the MRC and PATH. Other individuals having input into the study justifying authorship from MRCG at LSHTM, from collaborators and from PATH will similarly be included in publication(s). Additional publications resulting from the analysis of the study data will be agreed between PATH and the MRCG at LSHTM on a case-by-case basis but will generally include authors from both organizations. PATH will be acknowledged in all publications as the Sponsor of the trial.

If a written contract for the conduct of the study, which includes publication provisions inconsistent with this statement, is executed between PATH and the study site, that contract's publication provisions shall apply rather than this statement.

12. STATISTICAL DESIGN AND ANALYSIS

This section describes study size calculations and the planned analysis of study objectives as envisioned at the time of the protocol. Any substantive changes to these planned analyses (e.g., definitions of analysis populations, endpoint definitions, or analysis methods) will be documented in a detailed Statistical Analysis Plan (SAP) developed and approved prior to interim unblinding of the CRO statistical personnel.

12.1. Sample Size Considerations

Previous clinical studies have provided the necessary immunogenicity, safety, and tolerability data to support WHO pre-qualification (PQ) of PNEUMOSIL. The current study is intended to provide additional data to assist WHO-PQ and regulatory authorities in making recommendations regarding the immunogenicity and safety of PNEUMOSIL when delivered in a 2+1 dosing schedule. Since there are no hypothesis tests specified in this supportive study, sample size considerations are based on expected

precision of immunogenicity-related parameter estimates, rates of AEs, and descriptive comparisons between treatment groups in these measures, which are considered sufficient by the study team to generate actionable data by regulatory authorities.

All sample size calculations assume the use of descriptive 95% CIs (both for treatment group-specific measures and differences between groups), with no adjustment for multiple comparisons. Unless otherwise noted, asymptotic Wald-type CIs will be used when describing proportions, and asymptotic likelihood Score-type intervals for differences in proportions. Log-normality will be assumed when computing CIs for GMCs, GMTs, and their ratios between groups.

Primary Immunogenicity Objective:

The VAC-056 study observed coefficients of variation (CV) that ranged from 0.89 to 1.46 for serotype-specific serum IgG antibody levels measured 4 weeks after a booster dose of PNEUMOSIL in infants. In the VAC-017 study, the variability of serotype-specific IgG antibody levels observed in infants boosted between approximately 10-14 months of age was consistent with this range. Assuming the CVs for all 10 PNEUMOSIL serotypes measured 4-weeks after booster in the current study are at most 1.5, then the lower and upper 95% confidence bounds for each serum IgG GMC are expected to be at most 14% below and 16% above the GMC based on the study size of 220 per group (assuming no more than 10% of subjects are not evaluable due to loss to follow-up or other exclusions) (Table 17). For example, if the observed serotype-specific GMC = 1.0 $\mu\text{g}/\text{mL}$, then the 95% confidence interval (CI) is expected to be no wider than (0.86, 1.16); if the GMC = 3.0 $\mu\text{g}/\text{mL}$ then the 95% CI is expected to be no wider than (2.58, 3.49). Similarly, the expected lower and upper 95% confidence bounds for descriptive GMC ratios (PNEUMOSIL versus either comparator) are expected to be no more than 19% below and 24% above the ratio. For example, if the observed GMC ratio equals 1.0, then the 95% CI is expected to be no wider than (0.81, 1.24), so long as the CV in the comparison group does not exceed 1.5.

Table 17. Expected precision of serotype-specific GMCs ($\mu\text{g/mL}$) and GMC ratios (PNEUMOSIL vs. reference) for a range of possible true GMCs and GMC ratios

GMC in PNEUMOSIL group	Expected 95% CI for GMC	GMC ratio (PNEUMOSIL vs. comparator)	Expected 95% CI for GMC Ratio [†]
0.5	0.43-0.58	0.75	0.60-0.93
		1.00	0.81-1.24
1.0	0.86-1.16	0.75	0.60-0.93
		1.00	0.81-1.24
3.0	2.58-3.49	0.75	0.60-0.93
		1.00	0.81-1.24
5.0	4.29-5.82	0.75	0.60-0.93
		1.00	0.81-1.24

[†] Precision of GMC ratio is independent of the GMC in column 1.

Secondary Immunogenicity Objectives

The precision of IgG GMCs at secondary time points is expected to be as for the primary objective, under the same assumptions about CV of serotype-specific IgGs and follow-up rates at different sampling times. The expected precision of other secondary immunogenicity objectives (IgG and OPA response rates, and OPA GMTs) is as follows:

Precision of IgG Response Rates and Differences in Rates

With a sample size of 220 per group (up to 10% of whom may not be evaluable), the half-width of 95% CIs for serum IgG response rates ($\text{IgG} \geq 0.35 \mu\text{g/mL}$ or $\text{IgG} \geq 1.0 \mu\text{g/mL}$) will be no more than 0.07, and the half-width of 95% CIs for differences in proportions should not exceed 0.10.

Precision of Serum OPA Titer Response Rates and Differences in Rates

With a sample size of 50 per group (and no more than 10% excluded), the half-width of 95% CIs for OPA response rates (titer $\geq 1:8$) will be no more than 0.15, and the half-width of 95% CIs for differences in proportions responding (PNEUMOSIL versus a comparator) should not exceed 0.21.

Precision of OPA GMTs and GMT ratios

The VAC-056 study observed CV values that ranged from 0.97 to 2.11 for serotype-specific OPA titers measured 4 weeks after a booster dose of PNEUMOSIL in infants. Assuming the CVs for all 10 PNEUMOSIL serotypes in the current study are at most 2.11 at any given secondary analysis time point, then the lower and upper 95% confidence bounds for each GMT are expected to be at most 32% below and 48% above the observed GMT based on the study size of 50 per group (assuming no more than 10% of subjects are not evaluable due to loss to follow-up or other exclusions). For example, if the observed serotype-specific GMT = 100, then the 95% CI is expected to be no wider than (68, 148). Similarly, the expected lower and upper 95% confidence bounds for descriptive GMT ratios

(PNEUMOSIL versus either comparator) are expected to be no more than 42% below and 73% above the ratio. For example, if the observed GMT ratio equals 1, then the 95% CI is expected to be no wider than (0.58, 1.73), so long as the CV in the comparison group does not exceed 2.11.

Safety

With a sample size of 220 infants vaccinated per group, there is an 89% chance of observing at least 1 safety endpoint (e.g., a solicited AE) which occurs with probability 0.01 or more; if no events of a specific classification occur then the 95% upper confidence bound for the event rate will be 0.017.

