12.4. Multiple Comparisons/Multiplicity

There will be no type I error control of multiple comparisons in this descriptive study. All tests will be two-sided and conducted at the 0.05 significance level, and a coverage level of 95% will be used for all confidence intervals.

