3.2.1. Primary Immunogenicity Objective: IgG GMCs 4-weeks Post Booster

The previous pivotal Phase 3 study of PNEUMOSIL (VAC-056) in infants observed coefficients of variation (CV) that ranged from 0.89 to 1.46 for serotype-specific serum IgG antibody concentrations 4-weeks after a booster dose. Assuming the CVs for all PNEUMOSIL serotypes measured 4-weeks after booster in the current study are at most 1.5, the lower and upper 95% confidence bounds for each serum IgG GMC are expected to be at most 14% below and 16% above the observed GMC based on the study size of 220 per group (further assuming no more than 10% of subjects are non-evaluable due to loss to follow-up or other exclusions). For example, if the observed serotype-specific GMC = 1.0 µg/mL then the 95% CI is expected to be no wider than (0.86, 1.16) (Table 2). Similarly, the expected 95% bounds for descriptive GMC ratios (PNEUMOSIL versus either comparator) are expected to be no more than 19% below and

24% above the ratio. For example, if the observed GMC ratio equals 1.0, then the 95% CI is expected to be no wider than (0.81, 1.24), so long as the CV in the comparison group does not exceed 1.5.

Table 2. Expected precision of serotype-specific GMCs and GMC ratios (PNEUMOSIL vs. comparator) for a range of possible true GMCs and GMC ratios

GMC in PNEUMOSIL group	Expected 95% CI for GMC	GMC Ratio (PNEUMOSIL vs. comparator)	Expected 95% CI for GMC Ratio
0.5	0.43-0.58	0.75	0.60-0.93
		1.00	0.81-1.24
		1.33	1.08-1.67
1.0	0.86-1.16	0.75	0.60-0.93
		1.00	0.81-1.24
		1.33	1.08-1.67
3.0	2.58-3.49	0.75	0.60-0.93
		1.00	0.81-1.24
		1.33	1.08-1.67
5.0	4.29-5.82	0.75	0.60-0.93
		1.00	0.81-1.24
		1.33	1.08-1.67

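### The primary IgG precision bounds are too narrow for type 14, and for the type 19A ratio to Synflorix, judged by the protocol's own VAC-056 post-booster data

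*Protocol*

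**What the plan says.** Protocol 12.1 states that the study has no hypothesis tests, so its size rests on expected precision and on adverse event rates. For intervals, "Log-normality will be assumed when computing CIs for GMCs, GMTs, and their ratios between groups", and "a coverage level of 95% will be used for all confidence intervals".

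The planning CV comes from VAC-056, where CVs "ranged from 0.89 to 1.46 for serotype-specific serum IgG antibody levels measured 4 weeks after a booster dose of PNEUMOSIL". The protocol adds that VAC-017 variability was consistent with that range. It then continues: "Assuming the CVs for all 10 PNEUMOSIL serotypes measured 4-weeks after booster in the current study are at most 1.5", the limits for each GMC "are expected to be at most 14% below and 16% above the GMC based on the study size of 220 per group", allowing for 10% non-evaluable. Ratio limits are put at no more than 19% below and 24% above, "so long as the CV in the comparison group does not exceed 1.5". Protocol Table 17 tabulates these figures. SAP 3.2.1 and its Table 2 carry the same claim, with limits "expected to be at most 14% below and 16% above the observed GMC".

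For other visits, Protocol 12.1 says "The precision of IgG GMCs at secondary time points is expected to be as for the primary objective", given the same CV and follow-up assumptions. SAP 3.2.3 says the same for V4.

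Protocol 1.8.2, Table 10, gives VAC-056 IgG GMCs with 95% CIs and group sizes after the booster. Table 8 gives them after the primary series.

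**The concern.** A 95% CI for a geometric mean, together with its n, determines the log-scale SD. Table 10 therefore allows a direct check of the planning CV in the study and at the time point from which that CV was taken. For type 14 the printed interval is wider than any CV in the quoted range allows.

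The bounds are offered as maxima over all ten serotypes, and they are the stated immunogenicity basis for 220 per group. If the sponsor's prior data already show the underlying assumption failing for a named serotype, a reader of Table 17 will expect tighter type 14 and 19A comparisons than the trial is likely to give.

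**Working it through.** **Inputs.** 220 per group with 10% non-evaluable gives n = 198. Planning CV 1.5 and two-sided 95% intervals (Protocol 12.1 and 12.4). GMCs, CIs and group sizes come from Protocol Tables 8 and 10.

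**Formulas.**
- Log SD from a CV: s = sqrt(ln(1 + CV²)).
- GMC limits: exp(± t·s/√n).
- Ratio limits: exp(± t·sqrt((s₁² + s₂²)/n)).
- Log SD from a printed CI: s = ln(U/L)/(2t)·√n, then CV = sqrt(exp(s²) − 1).

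**Step 1: the plan's own figures.** CV 1.5 gives s = sqrt(ln 3.25) = 1.0857. With n = 198, the GMC limits are 14.1% below and 16.4% above, and the ratio limits 19.3% and 23.9%. Normal quantiles give the same rounded values. This matches the text, the four GMC rows of Table 17 and its row for a ratio of 1.00. So the plan treats the CV as a log-normal CV.

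**Step 2: type 14, PNEUMOSIL, Table 10.** n = 420, CI 6.09 to 7.70. ln(7.70/6.09) = 0.2346, so s = 1.223 and CV = 1.86. Moving each limit by ±0.005 for rounding gives 1.84 to 1.88. A CV of 1.46 (s = 1.068) would have given about 6.18 to 7.59.

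**Step 3: expected precision at 198 per group with Table 10 log SDs** (percent below/above).

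| Serotype | PNEUMOSIL log SD (CV) | GMC limits | Synflorix log SD (CV) | Ratio, separate SDs | Ratio, pooled SD from Table 10 ratio CI |
|---|---|---|---|---|---|
| 14 | 1.223 (1.86) | 15.7/18.7 | 1.264 (1.98) | 21.8/27.9 | 21.4/27.2 |
| 19A | 0.920 (1.15) | 12.1/13.8 | 1.378 (2.38) | 20.7/26.0 | 19.3/23.9 |
| 6A | 1.051 (1.42) | 13.7/15.9 | 1.234 (1.89) | 20.3/25.4 | 19.8/24.6 |
| Other seven | CV 0.95 to 1.24 | at most 12.6/14.5 | CV 0.86 to 1.16 | at most 17.0/20.5 | at most 17.2/20.8 |

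With all 220 evaluable, the type 14 GMC limits are still 15.0% and 17.6%.

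**Step 4: rounding of the printed limits.** At the most favourable end, the type 14 ratio is still 21.7%/27.7% and 19A still 20.2%/25.3%. For 6A the Synflorix CI (0.35 to 0.49) is coarse: the CV could be 1.64 to 2.18, and the ratio could be as narrow as 19.4%/24.1%, which rounds to the stated bound.

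**Step 5: pooled or separate SDs for 19A.** The pooled SD behind Table 10's ratio CI is weighted about 2:1 towards PNEUMOSIL (423 against 205). With separate SDs, (422 × 0.920² + 204 × 1.378²)/626 = 1.19, so s is about 1.09. That weighting brings 19A to the stated limit. With equal groups, as planned here, the pooled variance is the plain average of the two variances and gives the separate-SD result.

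**Step 6: V4, Table 8, type 6B.** PNEUMOSIL (n = 1452, 1.13 to 1.30) gives s = 1.361, CV about 2.3. Synflorix (n = 724, 1.02 to 1.25) gives s = 1.393, CV about 2.4. At 198 per group: GMC 17.4%/21.0%, ratio 23.8%/31.3%. Rounding allows CVs as low as 2.0 and 2.2, or a PNEUMOSIL log SD as high as 1.44 (GMC about 18%/22%).

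**The case against.** The strongest reply is that nothing stated is false. Every bound carries its condition, and the arithmetic follows from it. That stands as far as it goes: a reader might infer a calculation error, and there is none. But the condition is the planning assumption, and Table 10 shows it failing for PNEUMOSIL type 14 and for Synflorix types 14 and 19A.

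A reader might also infer that the quoted range of 0.89 to 1.46 is wrong. The documents do not support that. They do not say whether these are raw-scale sample CVs or CVs derived from log SDs, and raw CVs can differ from Table 10's implied values without contradiction. The point does not depend on which they are. If raw, converting them to a log SD under log-normality does not recover type 14's variability; if log-scale, the range omits type 14. The reported consistency with VAC-017 cannot be checked, because the documents give no VAC-017 post-booster intervals.

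Three further limits stand. The 6A ratio cannot be called a failure, given rounding. Table 8 follows three primary doses, whereas V4 here follows two, so Step 6 is indicative only. Table 10 also follows a 3-dose primary series, but it is the source the protocol itself chose for the post-booster CV.

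Finally, the consequence is small. IgG has no margin or success rule, and reported CIs will use the observed SDs.

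**Conclusion.** The concern holds for named serotypes. Post booster, PNEUMOSIL type 14 is expected to give GMC limits of about 16% below and 19% above, against 14% and 16% stated. Ratios to Synflorix are about 22%/28% for type 14 and 21%/26% for 19A, against 19%/24%; 19A is near the stated limit if Table 10's pooled SD is used. Type 6A versus Synflorix is marginal. The other nine PNEUMOSIL GMCs meet the stated bound, 6A narrowly. The excess is 2 to 3 points on a GMC and up to 4 on a ratio.

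This assumes that VAC-056 variability carries over, as the plan itself assumes, and 198 evaluable per group.

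Two stronger readings are not supported. One is that the trial is too small. Restoring the stated type 14 GMC bound would take about 251 evaluable per group (198 × (1.223/1.0857)²), but no test or decision depends on that bound, and the size also rests on safety and response-rate precision. The other is that the Prevenar 13 ratios miss the bound as well. The documents give no post-booster Prevenar 13 IgG intervals, so that cannot be judged either way.

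**What to change.** In Protocol 12.1/Table 17 and SAP 3.2.1/Table 2:
- Derive precision from the log SDs behind Table 10, and drop the CV of 1.5 as a ceiling for all serotypes.
- Restate post-booster precision for the worst serotype as about 16%/19% for GMCs and 22%/28% for ratios to Synflorix.
- State that the precision of ratios to Prevenar 13 is an assumption.

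In Protocol 12.1 (secondary objectives) and SAP 3.2.3:
- Drop the statement that V4 precision equals the primary.
- Note that 3-dose VAC-056 data for 6B suggest roughly 17%/21% for the GMC and 24%/31% for the ratio to Synflorix, as indicative values and not maxima.
- The protocol sentence also covers the pre-booster visit (V5), for which the documents give no intervals; label that precision an assumption.

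The cost is restated text and two tables, with slightly less favourable figures. Enrolment and the analysis methods do not change.

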
Abbreviations: CI=confidence interval; GMC=geometric mean concentration; IgG=immunoglobulin G

Source: VAC-056 Final Statistical Report Table 14.2.2-3.3.2

Table 11. Functional Antibody Response Post Booster: Treatment Group OPA Geometric Mean Titers and Treatment-Group Geometric Mean Titer Ratios (VAC-056)

Serotype	n	PNEUMOSIL (N=99)		Synflorix (N=100)		Treatment group comparison: PNEUMOSIL/Synflorix		
		GMT	(95% CI)	GMT	(95% CI)	GMT Ratio	(95% CI)	
Type 1	98	344.53	(261.77 – 453.46)	97	187.16	(141.59 – 247.40)	1.84	(1.25 – 2.72)
Type 5	99	409.87	(312.35 – 537.84)	100	360.59	(281.89 – 461.25)	1.14	(0.79 – 1.64)
Type 6A	98	3063.37	(2328.56 – 4030.06)	95	44.98	(25.86 – 78.25)	68.10	(37.07 – 125.09)
Type 6B	98	2824.56	(2207.88 – 3613.50)	100	1610.81	(1276.29 – 2033.01)	1.75	(1.25 – 2.46)
Type 7F	99	6977.27	(5601.56 – 8690.85)	100	4036.08	(3270.20 – 4981.32)	1.73	(1.28 – 2.34)
Type 9V	98	1137.28	(862.30 – 1499.94)	100	1229.05	(979.30 – 1542.50)	0.93	(0.65 – 1.32)
Type 14	97	3114.71	(2331.38 – 4161.22)	99	1411.94	(978.24 – 2037.92)	2.21	(1.38 – 3.51)
Type 19A	97	645.56	(489.69 – 851.04)	95	51.47	(32.40 – 81.76)	12.54	(7.36 – 21.37)
Type 19F	99	1592.40	(1255.72 – 2019.35)	98	1580.46	(1189.81 – 2099.38)	1.01	(0.70 – 1.46)
Type 23F	99	3846.82	(2962.23 – 4995.58)	100	1226.89	(967.91 – 1555.18)	3.14	(2.21 – 4.45)

Abbreviations: CI=confidence interval; GMT=geometric mean titer; OPA=opsonophagocytic activity

Source: VAC-056 Final Statistical Report Table 14.2.2-3.4.2

Post-booster OPA GMTs were significantly higher in the PNEUMOSIL group for 7 serotypes (1, 6A, 6B, 7F, 14, 19A, 23F). There was no serotype with significantly higher OPA GMT in the Synflorix group (Table 11).

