3.2.3. Secondary Immunogenicity Objectives

The precision of IgG GMCs 4 weeks post completion of primary vaccination (V4) is expected to be as for the primary objective under the same assumptions about CV of serotype-specific IgGs and follow-up rates as previously described. The expected precision of other secondary immunogenicity objectives (IgG response rates, OPA response rates, and OPA GMTs) are as follows:

With a sample size of 220 per group (up to 10% of whom may not be evaluable), the half-width of 95% CIs for serum IgG response rates ($\text{IgG} \geq 0.35 \mu\text{g/mL}$ or $\text{IgG} \geq 1.0 \mu\text{g/mL}$) will be no more than 0.07, and the half-width of 95% CIs for differences in proportions should not exceed 0.10.

With a sample size of 50 per group (and no more than 10% excluded), the half-width of 95% CIs for OPA response rates (titer ≥ 8) will be no more than 0.15, and the half-width of 95% CIs for differences in proportions responding (PNEUMOSIL versus a comparator) should not exceed 0.21.

The VAC-056 study observed CV values that ranged from 0.97 to 2.11 for serotype-specific OPA titers measured 4 weeks after a booster dose of PNEUMOSIL in infants. Assuming the CVs for all 10 PNEUMOSIL serotypes in the current study are at most 2.11 at V4 and V6, the lower and upper 95% confidence bounds for each GMT are expected to be at most 32% below and 48% above the observed GMT based on the study size of 50 per group (assuming no more than 10% of subjects are not evaluable due to loss to follow-up or other exclusions). For example, if the observed serotype-specific GMT = 100, then the 95% CI is expected to be no wider than (68, 148). Similarly, the expected lower and upper 95% confidence bounds for descriptive GMT ratios (PNEUMOSIL versus either comparator) are expected to be no more than 42% below and 73% above the ratio. For example, if the observed GMT ratio equals 1, then the 95% CI is expected to be no wider than (0.58, 1.73), so long as the CV in the comparison group does not exceed 2.11.

Due to positive within-subject correlation among subjects contributing both V4 and V6 data, the precision of within-group booster-effects (ratios of GMCs and GMTs post-booster versus post-primary series) is expected to be at least as high as that of the between-group contrasts at V4 or V6 described above, under similar assumptions about CV and the percentage of evaluable subjects.

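### The post-booster OPA variability (CV 0.97 to 2.11) conflicts with the protocol's own Table 11, so the stated V6 precision for GMTs and GMT ratios is too favourable

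*Protocol*

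**What the plan says.** Protocol 12.1, under the precision of OPA GMTs and GMT ratios, cites the pivotal trial's PNEUMOSIL recipients: "The VAC-056 study observed CV values that ranged from 0.97 to 2.11 for serotype-specific OPA titers measured 4 weeks after a booster". It then plans on the upper end: "Assuming the CVs for all 10 PNEUMOSIL serotypes in the current study are at most 2.11 at any given secondary analysis time point". The evaluable number, 45 per group, follows from this clause, which goes on to cover further reasons for exclusion: "based on the study size of 50 per group (assuming no more than 10% of subjects are not evaluable due to loss to follow-up or". The intervals are two-sided 95%, and "Log-normality will be assumed when computing CIs for GMCs, GMTs, and their ratios between groups".

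The resulting GMT limits are "at most 32% below and 48% above the observed GMT". Ratio limits are "expected to be no more than 42% below and 73% above the ratio" (SAP 3.2.3, same figures as the protocol), provided the comparator CV is no more than 2.11. The SAP applies the assumption at V4 and V6.

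Protocol 1.8.2 contains Table 11, titled "Functional Antibody Response Post Booster: Treatment Group OPA Geometric Mean Titers" and the corresponding ratios for VAC-056. It gives a GMT, 95% CI and n for each serotype and arm.

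**The concern.** Table 11 and the CV range describe the same data: VAC-056, PNEUMOSIL recipients, OPA titers, 4 weeks after the booster. A 95% CI for a GMT with a known n fixes the log-scale SD, so the two can be compared directly, and they disagree at both ends of the range.

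Protocol 12.1 specifies no hypothesis tests and justifies the sample size by expected precision. For Secondary Objective 1 (post-booster OPA GMTs and ratios), these limits are therefore the whole case for 50 subjects per group. SAP 5.3.1 also calls a difference statistically significant when the ratio CI excludes 1, so interval width affects what can be concluded.

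The point concerns V6 and the post-booster input itself, not the use of that input at V4.

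**Working it through.** **Step 1. Reproduce the plan's figures.** Inputs: CV 2.11, n = 45 per group, log-normality, t quantiles.

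- Log SD = √ln(1 + CV²) = √ln(1 + 2.11²) = 1.302.
- GMT limits = exp(± t(44) × 1.302/√45), with t = 2.015: 0.676 to 1.479. Stated: 32% below / 48% above.
- Ratio limits = exp(± t(88) × 1.302 × √(2/45)), with t = 1.987: 0.579 to 1.726. Stated: 0.58 to 1.73.

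The arithmetic is right, and it shows that 2.11 was used as a log-normal CV.

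**Step 2. Recover the log-scale spread from Table 11.** For each arm and serotype with CI (L, U) and n observations:

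- SD = ln(U/L) / (2 × t(0.975, n−1)) × √n
- CV = √(exp(SD²) − 1)

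Example, PNEUMOSIL type 14: n = 97, CI 2331.38 to 4161.22, giving SD 1.437 and CV 2.63.

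**Step 3. Recompute the limits at n = 45.** The GMT column uses the PNEUMOSIL SD. The ratio column uses each arm's own SD: exp(± t(88) × √((SD₁² + SD₂²)/45)).

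| Serotype | PNEUMOSIL SD / CV | Synflorix SD / CV | GMT limits | Ratio limits |
|---|---|---|---|---|
| 1 | 1.370 / 2.35 | 1.384 / 2.41 | 0.663–1.509 | 0.562–1.781 |
| 5 | 1.362 / 2.32 | 1.241 / 1.91 | 0.664–1.506 | 0.579–1.726 |
| 6A | 1.368 / 2.34 | 2.718 / 40 | 0.663–1.508 | 0.406–2.463 |
| 6B | 1.229 / 1.88 | 1.173 / 1.72 | 0.691–1.446 | 0.605–1.654 |
| 7F | 1.101 / 1.54 | 1.060 / 1.44 | 0.718–1.392 | 0.636–1.573 |
| 9V | 1.381 / 2.39 | 1.145 / 1.65 | 0.660–1.514 | 0.588–1.701 |
| 14 | 1.437 / 2.63 | 1.840 / 5.34 | 0.649–1.540 | 0.501–1.997 |
| 19A | 1.371 / 2.36 | 2.272 / 13.2 | 0.662–1.510 | 0.456–2.195 |
| 19F | 1.191 / 1.77 | 1.416 / 2.54 | 0.699–1.430 | 0.578–1.730 |
| 23F | 1.310 / 2.14 | 1.195 / 1.78 | 0.675–1.482 | 0.591–1.691 |

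- The PNEUMOSIL CVs run from 1.54 to 2.63. Seven of ten exceed 2.11 (23F only marginally), and none is near 0.97.
- Six GMT upper limits exceed +48%: types 1, 5, 6A, 9V, 14 and 19A. Type 23F meets it within rounding.
- Five Synflorix CVs exceed 2.11 (types 1, 6A, 14, 19A, 19F), so the condition on the ratio limits fails there. Four ratios then exceed +73% (1, 6A, 14, 19A), and 19F sits at the limit.
- With the comparator held at exactly CV 2.11, six ratios still exceed +73% (types 1, 5, 6A, 9V, 14, 19A, with upper limits 1.75 to 1.78), because of PNEUMOSIL's own spread.

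**Step 4. Check the back-calculation.** For type 14, the two SDs with the Table 11 sample sizes give a log-ratio SE of √(1.437²/97 + 1.840²/99) = 0.236. The printed ratio CI (1.38 to 3.51) gives 0.237. For 6A, the half-widths on the log scale are 0.614 from the SDs and 0.608 from the printed CI. The table is internally consistent.

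**Step 5. Illustrate the consequence.** For type 14 at 45 per group, the log-ratio SE is √((1.437² + 1.840²)/45) = 0.348, against 1.302 × √(2/45) = 0.275 under the plan. At an assumed true ratio of 0.5, the chance that the 95% CI excludes 1 falls from about 70% to about 50%.

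**The case against.** **The CV scale is undefined.** The 0.97 to 2.11 range could be a raw SD divided by the mean, which can coexist with Table 11 if titers are not exactly log-normal. The VAC-056 report is not available, so the source figure cannot be called wrong in itself. This stands as a possible explanation. It does not rescue the limits, because the plan converted 2.11 as a log-normal CV.

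**45 per group is the floor.** SAP 3.5 provides for replacements and allows further specimens to be tested. With all 50 evaluable, only the type 14 GMT clearly misses (1.505), and with the comparator at CV 2.11 every ratio is within +73% (worst 1.723). That is correct, but the plan states its limits as maxima that allow for 10% exclusions. Even at 50, the Synflorix ratio for type 14 is 0.52 to 1.93.

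**The ratio statement is conditional, and the largest misses are 6A and 19A.** Synflorix does not contain these serotypes, and Table 11 shows ratios of 68 and 12.5, so wider intervals would not hide the difference. That is fair. Type 14, however, is in both vaccines, and the condition on the comparator does not cover the GMT limits.

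**Little depends on it.** These are descriptive secondary endpoints with no margin or success criterion, actual intervals will be reported, and the true ratio of 0.5 is a chosen scenario (Table 11 shows 2.21 for type 14). This limits the weight of the point but does not make the stated limits right.

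**Conclusion.** The concern holds. The arithmetic in Protocol 12.1 and SAP 3.2.3 is correct, but its variability input does not match the log-scale spread in Table 11, and the stated maxima are not met on the protocol's own data.

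The shortfall for PNEUMOSIL GMTs is modest: about 51% above for five serotypes and 54% for type 14, against 48%. It is material for the Synflorix ratios of types 14, 19A and 6A and slight for type 1 (44% below / 78% above). Using Synflorix's own spread, the ratio limits hold for types 5, 6B, 7F, 9V and 23F, with 19F at the limit.

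This rests on 45 evaluable per group, log-normality, and VAC-056 variability (three primary doses plus booster) carrying over to the 2+1 schedule. The plan relies on the same study. The documents give no post-booster OPA spread for Prevenar 13, so precision for that comparison cannot be checked.

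**What to change.** In Protocol 12.1 and SAP 3.2.3, replace the 0.97 to 2.11 range with the log-scale SDs implied by Table 11: PNEUMOSIL 1.10 to 1.44; Synflorix 1.06 to 1.84 for the eight shared serotypes, 2.72 for 6A and 2.27 for 19A. If a CV is still quoted, say what scale it is on.

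Restate V6 precision at 45 per group: GMT up to 35% below / 54% above; ratio to Synflorix up to 50% / 100% for shared serotypes, 54% / 119% for 19A and 59% / 146% for 6A. Label the Prevenar 13 ratio precision as resting on an assumed spread.

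The cost is wording in two sections, with no added subjects or assays; the stated precision becomes less favourable. Keeping the present limits instead would need more OPA specimens: 55 evaluable per group for the type 14 GMT, and 71, 92 and 120 for the Synflorix ratios of types 14, 19A and 6A.
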